3.3 Inclusion of Women and Minorities

Both men and women of all races and ethnic groups are eligible for this trial.

4. REGISTRATION PROCEDURES

4.1 Patient Recruitment

Patients will be identified and recruited through Radiation Oncology, Urology, and Medical Oncology clinic consultations and follow-up visits at the University of Chicago

4.2 Patient Renumeration

Patients will receive no payment for participation in this trial.

5. TREATMENT PLAN

5.1 Study Design

This is a pilot study of the use of SBRT to all sites of disease for patients with oligometastatic RCC. Patients may receive off-protocol systemic therapy per medical oncologist discretion no earlier than 4 weeks after starting SBRT. While there are no restrictions on systemic therapy following SBRT, caution is advised on the use of bevacizumab given prior case reports demonstrating the possibility of heightened toxicity when this agent is used in the setting of SBRT. Limited or symptomatic recurrences can also be treated with radiation therapy (either SBRT or conventional therapy) at the clinician's discretion.

Enrollment will proceed according to a sequential toxicity monitoring schema to test the null hypothesis of a $\pi_0=5\%$ grade 4 toxicity rate against an upper acceptable boundary of a $\pi_1=20\%$ grade 4 toxicity rate. Trial enrollment will be halted if there are two grade 4 events within the first 2 patients, if there are three events within the first 14 patients, or if there are four events within the first 25 patients. The treatment will be considered successful if there are less than four events in 25 evaluable patients (<16%).

Treatment will be administered on an outpatient basis. The details of planning and administration of radiotherapy are discussed in detail in section 6. Reported adverse events and potential risks for SBRT are described in Section 8. Appropriate dose modifications for SBRT are described in Section 6. No investigational or commercial agents or therapies other than those described below may be administered with the intent to treat the patient's malignancy.

The pilot study will be considered successful if 25 patients are accrued, with less than 4 having Grade 4+ toxicity events after SBRT.

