5.2 Definition of Grade ≥ 4 RT-related Toxicity

The evaluation period of acute toxicity will be defined by the period of 90 days following the first fraction of RT. Of note, late grade ≥ 4 toxicity occurring beyond 90 days and through the one year of planned post-treatment follow-up will still have the ability to modify the trial design and accrual per the discretion of the primary investigator. Grade ≥ 4 toxicity will be defined

according to Common Toxicity Criteria version 4.0 (ctep.cancer.gov/reporting/ctc.html). Toxicities will be classified by a study committee as likely due to SBRT or non-radiotherapy-related based on review of nature of toxicity and the areas being treated with radiotherapy.

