5.6 Criteria for Removal from Study

Patients will be removed from study when one of the following criteria applies:

- Intercurrent illness that prevents administration of SBRT,
- Unacceptable adverse event(s),
- Death,
- Patient decides to withdraw from the study, or
- General or specific changes in the patient's condition render the patient unacceptable for further treatment in the judgment of the investigator/treating physician.

The reason for study removal and the date the patient was removed must be documented in the Case Report Form.

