7.1.6 Additional Adverse Events Associated with Radiation to the Spine

The possible acute and late toxicities of radiation to the spine will include those that affect radiation to the region of the body in which the spine is being treated (i.e. head and neck, chest, abdomen, pelvis). Additionally, rarely, patients could develop damage to the spinal cord or cauda equina resulting in severe neurologic dysfunction/paralysis.

7.1.7 Treatment of Adverse Events:

All attempts should be made to limit the symptoms and the overall impact of acute and late effects of radiation. Side effects of treatment may be treated per standard of care supportive agents.

8. Adverse Event Reporting

University of Chicago Reporting Guidelines

8.1 If the adverse event requires reporting, the Research Nurse or MD reports the adverse reaction to the Cancer Clinical Trials Office (CCTO) at [contact] by the end of the business day when he/she becomes aware of the event. Events occurring after business hours will be reported to the CCTO by 12 pm (noon) the next business day.

8.2 The following information is required when calling in the event:

- Caller's Name and Telephone Number
- Patient Initials
- Patient Medical Record Number
- IRB Protocol Number
- PI of Study
- Attending Physician
- Date of Event
- Description of Event (including grade of the event and attribution of the event and if the event required hospitalization)

8.3 E-mail is sent to the research nurse, attending physician and PI of the study informing them that adverse reaction notification has been received.

8.4 The University of Chicago's IRB Serious Adverse Event Form must be sent to the CCTO within **5 calendar days of event occurrence**. The UC IRB Serious Adverse Event form is available on-line at: <http://ors.bsd.uchicago.edu/HS/newirbforms>. This form must be typed. Once the forms are completed, the original is forwarded to the study PI to review and sign. The signed report is delivered to the QA Coordinator. A weekly report of delinquent or pending documents will be forwarded to the applicable person who reported the event. All delinquent reporting (greater than

10 days from event occurrence) must include documentation of reason for delinquency and may require implementation of an action plan.

8.5 Once the appropriate AE documents have been received, the CCTO forwards these to the IRB. A copy will be forwarded to the appropriate Research Nurse.

9. Data Safety and Monitoring

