12. STATISTICAL CONSIDERATIONS

12.1 Study Design/Endpoints

This is a pilot study of the use of 5-fraction SBRT for oligometastatic RCC. Patients enrolled in the study will be treated with SBRT to all sites of disease. Enrollment will proceed according to a sequential toxicity monitoring schema [69] to test the null hypothesis of a $\pi_0=5\%$ grade 4 toxicity rate against an upper acceptable boundary of a $\pi_1=20\%$ grade 4 toxicity rate. Trial enrollment will be halted if there are two grade 4 events within the first 2 patients, if there are three events within the first 14 patients, or if there are four events within the first 25 patients. The treatment will be considered successful if there are less than four events in 25 patients, i.e., $<16\%$ observed toxicities. This design has approximately 80% power (78.8%) to declare the treatment too toxic if the true grade 4 toxicity rate is $\pi_1=20\%$.

Patients will be followed for a total of one year after completion of the trial per protocol. Patients may be treated with off-protocol systemic therapy no earlier than 2 weeks after completion of RT. The primary endpoint is the rate of grade 4 RT-related toxicity with this treatment approach. Secondary endpoints include determining the toxicity profile of 5-fraction SBRT, determining the feasibility of 5-fraction SBRT based on normal tissue dosimetric constraints based on the organ site of involvement, describing the LeC, PFS, and patterns of failure of this approach, as well as to explore the feasibility of accrual and the adequacy of the eligibility criteria of this approach.

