12.4 Analysis of the Primary Endpoint

The primary endpoint is the rate of grade ≥ 4 RT-related toxicity with this treatment approach. RT-related toxicity will be recorded as specified in the study calendar (section 10). All toxicity will be determined to be RT-related or non-RT-related by the study committee.

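### The toxicity halting rule does not pause enrolment after a single SBRT-related death, and its halting sentence says grade 4 where the endpoint says grade ≥ 4

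*Combined protocol and SAP*

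**What the plan says.** Section 5.1 states the rule as "Trial enrollment will be halted if there are two grade 4 events within the first 2 patients, if there are three events" by patient 14, or four by patient 25. Section 12.1 repeats it ("Trial enrollment will be halted if there are two grade 4 events within the first 2 patients"), and the schema carries the same counts. All three name the events as grade 4.

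Elsewhere the event is wider. Section 5.1 defines success thus: "The pilot study will be considered successful if 25 patients are accrued, with less than 4 having Grade 4+ toxicity events after SBRT". Section 12.4 says: "The primary endpoint is the rate of grade ≥ 4 RT-related toxicity with this treatment approach". The synopsis has a different rule (three or more of the first 10 patients), also on grade ≥ 4 and also without a provision for a death.

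Several other safeguards bear on a death:

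- **Reporting (Section 8).** A reportable event reaches the trials office "by the end of the business day when he/she becomes aware of the event", or by noon on the next business day if it occurs after hours. The documents then go to the IRB.
- **Attribution (Section 5.2).** "Toxicities will be classified by a study committee as likely due to SBRT or non-radiotherapy-related". No deadline is given.
- **Review (Section 9).** A weekly GU oncology conference reviews toxicities, and a form is signed for each protocol.
- **Late toxicity (Section 5.2).** Grade ≥ 4 events after 90 days "will still have the ability to modify the trial design and accrual per the discretion of the primary investigator".
- **Removal (Section 5.6).** "Patients will be removed from study when one of the following criteria applies"; death is on that list, but the criteria act on the individual patient.

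**The concern.** None of these provisions requires enrolment to wait while a possibly SBRT-related death is examined. The counting rule responds to the number of events, not to their gravity. For a death within 90 days of the first fraction, the protocol does not say what happens to accrual unless a count boundary is crossed.

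Section 7 lists harms that could be fatal: tracheoesophageal fistula, vascular rupture, severe pneumonitis and bowel perforation. It rates them unlikely. If one did prove fatal, another patient could be enrolled for the same treatment before anyone had decided whether SBRT was the cause.

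The wording adds a second gap. The halting sentence says grade 4 while the endpoint and the success criterion include grade 5, so a literal reader could leave a death out of the halting count.

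**Working it through.** **1. The plan's own figure.** Inputs from Section 12.1: boundaries of 2 events by patient 2, 3 by patient 14 and 4 by patient 25; rates of 5% and 20%. An exact patient-by-patient binomial recursion, with each outcome known before the next enrolment, gives:

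| True rate | P(halt) | Expected enrolled |
|---|---|---|
| 5% | 5.00% | 24.48 |
| 10% (added here) | 27.42% | 22.24 |
| 20% | 78.84% | 15.32 |

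The stated power of 78.8% reproduces.

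**2. What the rule does with deaths alone, read as grade ≥ 4.** Every placement of the deaths among 25 patients was enumerated:

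- One death: C(25,1) = 25 placements, 0 halt.
- Two deaths: C(25,2) = 300 placements, 1 halts (patients 1 and 2).
- Three deaths: C(25,3) = 2,300 placements. All three among the first 14 gives C(14,3) = 364; patients 1 and 2 plus one of patients 15 to 25 gives 11. So 375 halt. In the other 1,925, a trial with no further event meets the success criterion.

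A temporary pause leaves these counts as they are. They describe the rule and do not measure the benefit of the fix.

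**3. Enrolment between a death and its review.** The weekly conference gives a gap of up to 7 days. The documents state no accrual rate, so 0.5, 1 and 2 patients per month are assumed. Expected enrolments x = rate × 7/30.44; chance of at least one = 1 − exp(−x).

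| Patients per month | x | Chance of at least one |
|---|---|---|
| 0.5 | 0.11 | 10.9% |
| 1 | 0.23 | 20.5% |
| 2 | 0.46 | 36.9% |

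**4. Per trial.** The documents give no SBRT death rate. Assume that 10% to 50% of grade ≥ 4 events are fatal. Expected deaths = rate × share × expected enrolled; multiplying by x gives an upper bound on patients enrolled in such gaps.

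| Grade ≥ 4 rate | Expected SBRT deaths | Patients enrolled in gaps, at most |
|---|---|---|
| 5% | 0.12 to 0.61 | 0.01 to 0.28 |
| 10% | 0.22 to 1.11 | 0.03 to 0.51 |
| 20% | 0.31 to 1.53 | 0.04 to 0.70 |

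For example, 0.05 × 0.10 × 24.48 = 0.122 and 0.122 × 0.115 = 0.014; at the other end, 0.20 × 0.50 × 15.32 = 1.532 and 1.532 × 0.460 = 0.70.

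**5. Ceiling on the cost of a pause.** Suppose that every disease death during accrual went unclassified until the conference and cost one week. Assume exponential survival with medians of 6 and 15 months (Section 2.1) and 32 months (Section 2.3, taken as a median), evenly spaced enrolment, and each patient counted for up to 12 months. Accrual spans 24 intervals.

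| Patients per month | Weeks of accrual | Deaths before the 25th enrolment (32 to 6 months) | Share of accrual time |
|---|---|---|---|
| 0.5 | 209 | 5.0 to 16.6 | 2% to 8% |
| 1 | 104 | 4.3 to 14.9 | 4% to 14% |
| 2 | 52 | 3.0 to 11.4 | 6% to 22% |

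**The case against.** The strongest reply is that the protocol already handles this. It is a single-centre study. Reportable events reach the trials office within about one business day, the principal investigator is notified, the IRB receives the documents, and all active studies are reviewed weekly. An investigator may pause accrual voluntarily at any time. A compulsory pause therefore adds at most about a week of protection before a review that would happen anyway. The estimated benefit is a fraction of a patient, on assumed accrual and fatality rates; the top of the range needs a 20% grade ≥ 4 rate with half of those events fatal.

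Most of this stands, and it is why the point ranks low. What remains is that the pause is optional. The written discretion over accrual in Section 5.2 concerns late toxicity only, and attribution has no deadline.

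A reader might infer more than the documents support:

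- **That the trial ignores deaths.** The endpoint is grade ≥ 4 and the success criterion says Grade 4+, so a death counts as one event on the evident intent. Only a literal reading of the halting sentence excludes it.
- **That a death would go unreviewed.** Sections 5.2, 8 and 9 provide reporting, attribution and weekly review.
- **That pooling grades 4 and 5, or the boundary itself, is an error.** Pooling is a legitimate choice, and the stated power is correct.

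**Conclusion.** The point holds as a cheap improvement of the lowest severity. That no single-death pause is written anywhere is certain from the text. The size of the benefit is not: 0.11 to 0.46 expected further enrolments per death rests on assumed accrual of 0.5 to 2 patients per month and a 7-day gap. The per-trial bound of 0.01 to 0.70 rests also on assumed fatal shares of 10% to 50% and grade ≥ 4 rates of 5% to 20%.

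One might go further and ask for a permanent stop at the first fatal event. The design does not support that. With assumed fatal shares of 10% to 50%, the chance of halting at an acceptable 5% rate would rise from 5.0% to between 15.1% and 47.3%. A temporary suspension leaves the boundary's operating characteristics unchanged.

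**What to change.** 1. In the schema and Sections 5.1 and 12.1, replace grade 4 with grade ≥ 4 in the halting sentence.
2. Add to Sections 5.1 and 12.1: *Any grade 5 event that the study committee has not classified as non-radiotherapy-related suspends enrolment until it is classified and reviewed at the next weekly GU phase I/II conference; the decision to resume is recorded on the Data Safety and Monitoring form.*
3. Report the number of SBRT-related deaths beside the result on fewer than 4 of 25.

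The boundary, the maximum of 25 patients, the success criterion and the 78.8% power are unchanged. The committee, conference and form already exist, so the change is protocol wording only. A death already classified as unrelated causes no pause, and patients already enrolled remain under Section 5.6.

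The cost is a pause of about one week per qualifying death, or longer if the committee has not classified it by the conference. With one-week pauses, the ceiling is about 2% to 22% of accrual time at 0.5 to 2 patients per month, reached only if every disease death stayed unclassified until the conference. Prompt classification keeps the cost well below that.

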5.2 Definition of Grade ≥ 4 RT-related Toxicity

The evaluation period of acute toxicity will be defined by the period of 90 days following the first fraction of RT. Of note, late grade ≥ 4 toxicity occurring beyond 90 days and through the one year of planned post-treatment follow-up will still have the ability to modify the trial design and accrual per the discretion of the primary investigator. Grade ≥ 4 toxicity will be defined

according to Common Toxicity Criteria version 4.0 (ctep.cancer.gov/reporting/ctc.html). Toxicities will be classified by a study committee as likely due to SBRT or non-radiotherapy-related based on review of nature of toxicity and the areas being treated with radiotherapy.

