2. To determine the feasibility of delivering 5-fraction SBRT per protocol based on proposed normal tissue constraints in a variety of organ sites. (i.e., the ability to treat >80% of enrolled patients according to protocol guidelines).
3. To describe treated lesion control (LeC), progression free survival (PFS), and patterns of failure.
4. To determine the feasibility of accrual and adequacy of eligibility criteria by defining the proportion of eligible cases of metastatic RCC presented at the weekly multidisciplinary genitourinary conference at the University of Chicago Medical Center.
5. To make a preliminary evaluation regarding potential biomarkers in patient serum which may be assessed in a follow-up study (e.g. genetic or immunologic biomarkers).

Study Design: This is a single-armed pilot study to estimate the rate of CTCAE v4.0 grade ≥ 4 RT-related toxicity of 5-fraction SBRT in patients with oligometastatic RCC. Eligible patients must have histologically or cytologically diagnosed RCC with 1-5 sites of metastases, including up to 3 brain metastases. Patients may present with metastatic disease, or have previously treated primary disease with metastatic recurrence. All sites of metastasis must be ≤ 6 cm, and patients with recurrent/unresected primary tumors are eligible as long as said tumor is ≤ 10 cm and there is a plan to treat the primary tumor with a local therapy. Patients may not have had any oncologic therapy within 1 month prior to enrollment, no prior history of bevacizumab, and any brain metastases must be addressed with surgery and/or radiotherapy prior to enrollment. Patients will be treated with SBRT (preferred dose 50 Gy/5 fractions) to all radiographic sites of gross disease, including the primary if it can not be addressed with non-radiotherapeutic local therapy. Patients can thereafter begin off-protocol systemic therapy per medical oncology discretion, but any therapy will occur no earlier than 2 weeks after completion of RT.

The first 10 patients enrolled on the study will be considered the "initial cohort." If ≥ 3 of these patients have a CTCAE v4.0 grade ≥ 4 RT-related toxicity, enrollment will be discontinued and the trial stopped, otherwise 5 additional patients will be accrued. Study investigators will determine whether treatment related toxicities are RT-related or non-RT-related.

Statistical Methods:

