Definition of primary outcome/endpoint: RT-related grade ≥ 4 toxicity will be determined on a case-by-case basis by the study group, taking into consideration the region treated with SBRT, timing of the toxicity, and the nature of the toxicity. Toxicities will be graded as per CTCAE v4.0 criteria.

Definition of secondary outcomes/endpoints: LeC will be defined as absence of clinical or radiographic progression per RECIST criteria. PFS will be defined as progression in the treated lesion, organ in which the treated lesion is present, distant failure, or death from any cause.

Analytic plan for primary objective: Rates of RT-related grade ≥ 4 toxicity will be recorded, time to RT-related grade ≥ 4 toxicity will be recorded, and freedom from RT-related grade ≥ 4 toxicity will be determined using the Kaplan-Meier method.

Analytic plan for secondary objectives: LeC and PFS will be estimated at 1 year using the Kaplan-Meier method.

Sample size justification: A sample size of 25 patients will be needed to assess the safety and appropriateness of this method, identify the optimal candidates, and optimal SBRT fractionation/dose for different clinical scenarios.

TABLE OF CONTENTS

	Page
SCHEMA	i
1. OBJECTIVES	1
1.1 Primary Objectives	1
1.2 Secondary Objectives	1
2. BACKGROUND	1
2.1 Metastatic Renal Cell Carcinoma	1
2.2 Oligometastasis	1
2.3 Stereotactic Body Radiotherapy in Oligometastasis	2
2.4 Rationale for current study	3
2.4.1 Rationale for Secondary Objectives	4
3. PATIENT SELECTION	4
3.1 Eligibility Criteria	4
3.2 Exclusion Criteria	5
3.3 Inclusion of Women and Minorities	6
4. REGISTRATION PROCEDURES	6
4.1 Patient Recruitment	6
4.2 Patient Renumeration	6
5. TREATMENT PLAN	6
5.1 Study Design	6
5.2 Definition of Grade ≥ 4 RT-related Toxicity	6
5.3 General Concomitant Medication and Supportive Care Guidelines	7
5.4 Duration of Therapy	7
5.5 Duration of Follow Up	7
5.6 Criteria for Removal from Study	7
6. RADIATION THERAPY	7
6.1 Simulation	7
6.2 Premedications	8
6.3 Target Volumes	8
6.4 Treatment Planning	8
6.5 Dose Specifications	8
6.6 Critical Structures	9
6.7 RT Treatment	13
6.8 Radiotherapy Adverse Events	13
7. RISKS AND BENEFITS	13
7.1 Radiotherapy Adverse Events	13
8. Adverse Event Reporting	15
9. Data Safety Monitoring	16
10. STUDY CALENDAR	16
11. MEASUREMENT OF EFFECT	17
11.1 Antitumor Effect and Endpoints	17
11.2 Dosimetric description of delivery of Radiotherapy	18
12. STATISTICAL CONSIDERATIONS	19
12.1 Study Design/Endpoints	19

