5.4 Duration of Therapy

In the absence of treatment delays due to adverse events, radiotherapy should be completed within 1 month of the first day of radiotherapy (Day 28 of protocol treatment). Patients may receive systemic therapy off-protocol no earlier than 4 weeks after starting SBRT.

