Data Safety and Monitoring will occur at the weekly University of Chicago GU oncology phase I/II conference meetings, which are lead by senior level medical oncologists. At each meeting, all active studies will be reviewed for safety and progress toward completion. Toxicities and adverse events will be reviewed at each meeting and a Data Safety and Monitoring form will be completed for each protocol and signed by either the Principal Investigator, the Chairman of the Department or by his designate if the Chairman is not available.

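### The plan gives conflicting accounts of which grade 4 or higher events drive the halting and success rules, and its attribution definition has no place for possibly related events

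*Combined protocol and SAP*

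**What the plan says.** Section 12.1 sets up the monitoring rule "to test the null hypothesis of a $\pi_0=5\%$ grade 4 toxicity rate" "against an upper acceptable boundary of a $\pi_1=20\%$ grade 4 toxicity rate". Enrolment halts at two events in the first 2 patients, three in the first 14 or four in the first 25. The events are described by grade alone in the schema and in the halting sentences of 5.1 and 12.1. Section 5.1 closes by judging success on fewer than four patients with Grade 4+ events after SBRT, which is a condition on time and not on cause. On performance, 12.1 states: "This design has approximately 80% power (78.8%) to declare the treatment too toxic" at a true rate of 20%.

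Other places add attribution. The endpoint sentence in 12.1, and section 12.4, make the primary endpoint RT-related toxicity. The halting text in the synopsis (Study Design) also counts RT-related events and adds: "Study investigators will determine whether treatment related toxicities are RT-related or non-RT-related". Under the synopsis endpoint definition, RT-related grade ≥ 4 toxicity "will be determined on a case-by-case basis by the study group", considering region, timing and nature. Section 5.2, headed as the definition, says: "Toxicities will be classified by a study committee as likely due to SBRT or non-radiotherapy-related based on review of nature of toxicity". Section 12.5 refers back to 5.2.

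On overlapping treatment, section 5.4 says: "Patients may receive systemic therapy off-protocol no earlier than 4 weeks after starting SBRT". Section 5.1 agrees. The synopsis and 12.1 instead give two weeks after completion of RT. Section 5.2 sets the acute window at 90 days from the first fraction.

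**The concern.** In a single-arm safety study the classification of each event largely determines the result. Three things are left open here.

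- **The count.** It is unclear whether the boundary applies to all grade 4 or higher events or only to RT-related ones.
- **The threshold.** Section 5.2 names likely and unrelated, with nothing between them and no default for doubtful cases. The other passages say RT-related without giving a degree of certainty.
- **The decider.** The synopsis names study investigators and a study group; 5.2, 12.4 and 12.5 name a study committee. Its membership is not described.

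Doubtful cases are foreseeable. Section 5.1 places no restriction on later systemic therapy and itself warns of heightened toxicity when one agent is used in the setting of SBRT. With a boundary of four events in 25 patients, reclassifying one event can change the trial's conclusion. Sections 12.4 and 12.5 plan no explicit all-cause grade ≥ 4 rate, so a reader of the results could not readily see the effect of attribution.

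**Working it through.** **Step 1. What is counted, place by place.**

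| Place | Event counted | Condition on cause |
|---|---|---|
| Schema; halting sentences in 5.1 and 12.1 | grade 4 | none |
| 5.1, closing success sentence | grade 4+ after SBRT | none (timing only) |
| Synopsis, halting sentence | grade ≥ 4 | RT-related |
| Synopsis endpoint definition; 12.4 | grade ≥ 4 | RT-related, no threshold stated |
| 12.1, endpoint sentence | grade 4 | RT-related, no threshold stated |
| 5.2 (referred to by 12.5) | grade ≥ 4 | likely due to SBRT, or not radiotherapy-related |

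These do not give one rule. A grade 4 event possibly due to SBRT and possibly due to a systemic agent counts under the first two rows, is undetermined under the next three, and has no class under the last.

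**Step 2. Reproduce the stated power.** Inputs from 12.1: boundaries 2 in 2, 3 in 14 and 4 in 25; rates 5% and 20%. Let A, B and C be the events among patients 1–2, 3–14 and 15–25, with A ~ Bin(2, p), B ~ Bin(12, p) and C ~ Bin(11, p). Enrolment is not halted if A ≤ 1, A + B ≤ 2 and A + B + C ≤ 3. So

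P(halt) = 1 − Σ(a = 0 to 1) Σ(b = 0 to 2 − a) P(A = a) P(B = b) P(C ≤ 3 − a − b).

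- p = 0.20: 0.7884, matching the stated 78.8%.
- p = 0.05: 0.0500.

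Checking after every patient gives the same values. A single look at 25 patients would give 0.7660 at 20%, so 78.8% is the sequential figure.

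**Step 3. Missed events.** Suppose a share m of true SBRT events is not counted. The counted rate is 0.20 × (1 − m). The documents give no m; these values are assumed.

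| m | Counted rate | P(halt) |
|---|---|---|
| 0% | 20% | 78.8% |
| 5% | 19% | 75.2% |
| 10% | 18% | 71.1% |
| 20% | 16% | 61.7% |
| 25% | 15% | 56.5% |

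**Step 4. Events wrongly counted.** Suppose unrelated grade ≥ 4 events are counted in a share x of patients, independently (also assumed). At a true SBRT rate of 5% the counted rate is 1 − 0.95 × (1 − x).

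- x = 0: false halting 5.0%.
- x = 2%: 1 − 0.95 × 0.98 = 6.9%; false halting 11.6%.
- x = 5%: 1 − 0.95 × 0.95 = 9.75%; false halting 26.0%.

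Both errors can occur together. At a true 20% rate with m = 20% and x = 5%, the counted rate is 1 − 0.84 × 0.95 = 20.2% and P(halt) is 79.5%.

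**Step 5. Overlap with systemic therapy.** Starting at 28 days leaves 90 − 28 = 62 of the 90 days (69%). If RT ends at the day-28 limit and two weeks are added, 90 − 42 = 48 days remain (53%). Overlap is possible under either timing. The documents do not say how many patients will start systemic therapy.

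**The case against.** A reader might infer that an event enters the stopping count only if it is judged likely due to SBRT, and that the rule therefore loses much of its 78.8% power. The documents do not support that. The halting sentences in 5.1 and 12.1 carry no attribution condition, and the likely wording appears as a criterion only in 5.2. No passage sends doubtful events to the non-RT class; a cautious committee could count them. The missed shares are assumptions, and so is any view that overlapping causes will be common. If the 20% means the rate of events as adjudicated, 78.8% is unaffected. Step 4 also shows that error can run upward and can offset the loss, so a downward bias is not established.

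Nor do the documents say that the deciders are the treating physicians or that they know the running count. There are other checks: under section 8, reportable events go to the trials office with grade and attribution, and the documents are forwarded to the IRB; under section 9, toxicities are reviewed weekly, with a form "signed by either the Principal Investigator, the Chairman of the Department or by his designate". Investigator attribution is a defensible choice in a 25-patient pilot, and confirmation by members who did not treat the patient is a preference. An all-cause rate could be tabulated from what is collected, since 12.4 has all toxicity classified.

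These points stand. They do not settle which events count or how a possible event is handled. Reading the 20% as an adjudicated rate preserves the power figure only by leaving its meaning dependent on an undefined threshold.

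**Conclusion.** The concern holds as an inconsistency in the counting rule and a gap in the attribution definition, and should be corrected. That part rests on the text alone.

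The effect on power is conditional. It requires that the RT-related reading governs, that possible events are placed in the non-RT class, and that some of them are truly due to SBRT. Under those conditions, an assumed 10% to 25% of missed events lowers the chance of declaring a 20% rate too toxic by about 8 to 22 percentage points; a 5% miss costs under 4 points. The calculation shows that the rule is sensitive to attribution. It does not show that power will be lost or which way the net error will run.

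**What to change.** 1. State one counting rule in the synopsis, 5.1, 5.2, 12.1 and 12.4, and align the schema with it: a grade ≥ 4 event counts toward halting and success if possibly, probably or definitely related to SBRT, and is excluded only when a specific other cause is documented.
2. Name one body that decides, and use that name throughout.
3. Report the all-cause grade ≥ 4 rate beside the RT-related rate, each split by whether systemic therapy had started. The study calendar already collects adverse events and concurrent medications at every on-treatment and follow-up visit.
4. Show the operating characteristics under the chosen rule, with a range for missed and for wrongly counted events.
5. Reconcile the two timings for systemic therapy (four weeks after starting SBRT; two weeks after completing RT).

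The direct cost is wording, one extra table and a short calculation; no new data are needed. The statistical cost is more false halting, by the amounts in Step 4, if unrelated events are swept in. The documented-cause exclusion limits this, but the sponsor should state the trade-off and accept it explicitly.
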